- 3) Kellgren-Lawrence grade 1-3 based on a radiograph within 6 months of presentation to the clinic
- 4) Symptomatic evidence of tibiofemoral osteoarthritis for ≥ 6 months
- 5) Average numeric pain rating of 4 – 8 on a scale of zero to 10 (defined as moderate level) over the past week

6) Previous trial of 6 weeks minimum of conservative therapy including physical therapy, weight loss, anti-inflammatory medication, or injection therapy

Exclusion Criteria

- 1) Grade 4 KOA according to the Kellgren-Lawrence scale
- 2) History of intraarticular viscosupplementation or steroid injection in the target knee in the past 6 months at the time of the baseline visit or intraarticular injection planned during the trial
- 3) History of arthroscopic surgery in the target knee in the past 12 months at the time of presentation to the clinic or planned surgery during the trial period (e.g., scheduled for/awaiting arthroscopy or a knee replacement procedure)
- 4) Bilateral KOA (unless the contralateral knee involvement is limited to radiographic osteoarthritis and not symptomatic)
- 5) Ipsilateral (same side) or contralateral (opposite side) symptomatic osteoarthritis of hip or ankle
- 6) Clinically apparent tense effusion or other acute inflammation of the target knee at the time of presentation to the clinic
- 7) Active infection of either lower extremity such as cellulitis or any skin disease or infection in the area where BMAC is aspirated, blood is drawn, or an injection is given
- 8) History of diagnosis of any of the following: 1) septic osteoarthritis of any joint, 2) inflammatory arthropathy such as rheumatoid arthritis, gout, pseudogout, lupus, crystalline arthropathy, chondrocalcinosis and other rheumatology diagnoses
- 9) Cruciate/collateral knee ligament instability, ligament laxity, or meniscal instability of the target knee
- 10) Significant alignment deformity such as varus/valgus of the target knee in the judgment of the investigator
- 11) Currently pregnant, nursing, or planning to become pregnant during the trial period
- 12) Previous or known allergic reaction or hypersensitivity to heparin; sodium citrate; hyaluronan products or specifically Gel-One®; cinnamon; bird products such as feathers, eggs, or poultry; avian proteins
- 13) Not suitable for BMAC tissue allograft injection per physician (e.g., blood dyscrasia)

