A two-point change has been established as the minimal clinically important difference as measured by the NPRS.⁴² Each patient will have an average pain rating of 4-8 on a 0-10 scale over the past week prior to completion of baseline information to be included in the study.

- Change in the PROMIS Global Health scale (short form, version 1.1) at 3 months, 6 months, and 12 months post treatment (see appendix 4.3 for PROMIS Global Health scale short form, version 1.1)

The PROMIS Global Health scale (short form, version 1.1) will be useful to describe changes in the study population. The scale has been described as a useful summary of physical and mental health in clinical studies with patient-reported outcomes.⁴³

Study Variables Table:

Table 1. Study Variables.	
Category	Data points
Demographics	
 1. Age 2. Gender (0-male, 1-female) 3. BMI
Relevant clinical information or past medical history	
 1. Previous surgery on target knee (0-no, 1-yes) 2. Previous injection on target knee (0-no, 1-yes) 3. Previous physical therapy for target knee (0-no, 1-yes) 4. Onset/course of target knee pain (0-traumatic, 1- insidious) 5. Kellgren-Lawrence grade (0-grade 1, 1-grade 2, 2-grade 3) 6. Platelet count -Group A only (in thousands per ml of blood)
Other relevant therapies received following the study treatment	
 1. Pain medications for the target knee (0-no, 1-yes) 2. Over the counter medications for the target knee (0-no, 1-yes as needed, 2-yes daily) 3. Prescription anti-inflammatories or NSAIDs for the target knee (0-no, 1-yes as needed, 2-yes daily)

	
 4. Narcotics for the target knee (0-no, 1-yes as needed, 2-yes daily) 5. Physical therapy for the target knee (0-no, 1-yes)
Primary outcome measures	
 1. KOOS pain subscale 2. KOOS symptoms subscale 3. KOOS ADL subscale 4. KOOS sport and recreation subscale 5. KOOS quality of life subscale
Secondary outcome measures	
 1. NPRS 2. PROMIS Global Health scale score

2.4 – Study Design

Overall Design

This study will be a prospective, 1:1 randomized, controlled trial. The two treatment groups (Group A: BMAC and PRP injections and Group B: Gel-One® hyaluronate injection) will be compared to one another.

A study calendar is included within section 2.4 or can be found in Appendix 4.5.

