As described previously, the patients’ knee pain, function, and quality of life measures will be assessed via standardized survey tools (i.e., KOOS subscales, NPRS, and PROMIS Global Health scale) at baseline, 3 months, 6 months, and 12 months. The KOOS subscales (i.e., pain, symptoms, activities of daily living, function in sports and recreation, and knee related quality of life) combine for 42 questions in a 5 point rating scale format. The NPRS is a semantic differential scale ranging from zero (i.e., no pain) to ten (i.e., worst imaginable pain). The PROMIS Global Health scale (short form, version 1.1) is a five point rating scale consisting of 10 questions. The patient will independently complete each clinical scale once comprehension is assured. The research team member administering the clinical scales will be available to answer patient questions regarding completing the scale. This research team member will be unaware of group allocation.

Study Calendar

	Study Calendar							
	Presentation	Baseline ≤14d from presentation or at presentation	periodWithdrawal	Treatment ≤30d from Baseline	2-Weeks after treatment +/- 7d	3-Months after treatment +/- 7d	6-Months after treatment +/- 14d	12- Months after treatment +/- 14d
Screen for eligibility	x							
Informed consent		x						
Demographics		x						
Past Medical History		x						
KOOS subscales		x				x	x	x
NPRS		x				x	x	x
PROMIS		x				x	x	x
Other relevant						x	x	x

therapies								
Randomization		x						
CBC (Group A)		x						
Withdrawal ^a			x					
Treatment				x				
Visits	x	x		x	x	x	x	x
SAE Evaluation					x	x	x	x

^aNSAIDs or oral corticosteroids during the 2 weeks leading up to the treatment visit or platelet count <150,000 per microliter of blood or >450,000 per microliter of blood

Data Storage and Confidentiality

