We recognize that there is risk for inherent bias within our study as patients are unable to be completely blinded to type of treatment he/she receives because each treatment procedure is distinctly different. Risk of selection bias is minimized by use of a randomized allocation schedule. Risk of influence on the patient when completing clinical outcome scales will be negated as the research team member administering the clinical outcome tools at 3, 6, and 12 months post-treatment will be blinded to group allocation.

ClinicalTrials.gov

As this study meets the FDAAA 801 definition of an “Applicable Clinical Trial” based on a drug and biologic, it is required that the study be registered on ClinicalTrials.gov. The Principal Investigator will register and activate the study account prior to enrollment, and all results will be entered upon study completion, followings statistical analysis, per the Results Database Guidelines.

2.5 – Statistical Analysis

Aim 1: Change in mean KOOS subscale scores over time based on treatment group

Total scores will be calculated for each patient using the KOOS subscales. The validated analysis guidelines for the KOOS instrument will be used. Patient’s total scores will be compared at baseline, 3 months, 6 months, and 12 months post treatment and compared by treatment group.

The statistical method that will be used is a Repeated Measures ANOVA (RM-ANOVA). This statistical strategy will allow us to control for the correlation in each individual’s measurements over time. The use of the standardized scales ensures that the outcome variable will be normally distributed, which will meet the underlying assumptions of the RM-ANOVA analysis. We will use the KOOS subscale score as the dependent variable, and the treatment assignment as the independent variable. If the distribution of gender is unequal across treatment groups after randomization, this statistical method will allow us to control for gender because changes in score will differ by gender. We will also be able to control for clinically meaningful variables such as patient age or BMI if there are differences in these variables between the two treatment groups at baseline.

Aim 2a: Change in mean NPRS score over time based on treatment group

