Total scores will be calculated for each patient using the NPRS. The NPRS instrument will be processed using the tool’s validated analysis guidelines. Patient’s total scores will be compared at baseline, 3 months, 6 months, and 12 months post treatment and compared by treatment group.

The statistical method that will be used is a RM-ANOVA. This statistical strategy will allow us to control for the correlation in each individual’s measurements over time. The use of the standardized scales ensures that the outcome variable will be normally distributed, which will meet the underlying assumptions of the RM-ANOVA analysis. We will use the NPRS as the dependent variable, and the treatment assignment as the independent variable. If the distribution of gender is unequal across treatment groups after randomization, this statistical method will allow us to control for gender

because changes in score will differ by gender. We will also be able to control for clinically meaningful variables such as patient age or BMI if there are differences in these variables between the two treatment groups at baseline.

Aim 2b: Change in mean PROMIS – Global Health score based on treatment group

Total scores will be calculated for each patient using the PROM Global Health scale (short form, version 1.1). The PROMIS global health instrument will be processed using the tool's validated analysis guidelines. Patient's total scores will be compared at baseline, 3 months, 6 months, and 12 months post treatment and compared by treatment group.

The statistical method that will be used is a RM-ANOVA. This statistical strategy will allow us to control for the correlation in each individual's measurements over time. The use of the standardized scales ensures that the outcome variable will be normally distributed, which will meet the underlying assumptions of the RM-ANOVA analysis. We will use the PROMIS global health scale as the dependent variable, and the treatment assignment as the independent variable. If the distribution of gender is unequal across treatment groups after randomization, this statistical method will allow us to control for gender because changes in score will differ by gender. We will also be able to control for clinically meaningful variables such as patient age or BMI if there are differences in these variables between the two treatment groups at baseline.

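### Section 2.5 wrongly says standardized scales guarantee normal outcomes; type I error barely moves, but using the baseline score as an outcome level instead of a covariate loses precision

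*Combined protocol and SAP*

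**What the plan says.** Section 2.5 gives the same justification under Aims 1 (KOOS), 2a (NPRS) and 2b (PROMIS): "The use of the standardized scales ensures that the outcome variable will be normally distributed", and it concludes that the RM-ANOVA assumptions are therefore met. It names no residual check, sphericity check or correction, transformation or fallback.

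For NPRS, section 2.5 says that patients' "total scores will be compared at baseline, 3 months, 6 months, and 12 months post treatment and compared by treatment group", and "We will use the NPRS as the dependent variable, and the treatment assignment as the independent variable". Baseline is therefore one of four levels of the outcome. Gender, age and BMI may be adjusted for if the groups differ on them; the baseline score is not named as a covariate for any aim. Section 2.3 defines the outcomes as changes, but section 2.5 does not say that change scores are modelled.

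The inclusion criteria in section 2.1 require "Average numeric pain rating of 4 – 8 on a scale of zero to 10 (defined as moderate level) over the past week", and section 2.3 ties that band to the baseline forms: "Each patient will have an average pain rating of 4-8 on a 0-10 scale over the past week prior to completion of baseline information". Section 2.4 describes the NPRS as running from 0 to 10, and section 2.3 gives the KOOS subscale range as 0 to 100.

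**The concern.** Standardization governs how a scale is administered and scored. It says nothing about the distribution of the scores in a given population. For NPRS the plan's own entry rule works against the claim, because one of the four repeated measurements is confined, or nearly so, to the middle of the scale. That measurement will be non-normal and less variable than the other three, which strains both normality and sphericity.

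Two things could be at stake with 15 patients per arm: the error rate of the tests, and the precision of the treatment comparison. The sentence also stands where a check would normally be specified, so the analyst has no pre-specified course if the residuals look poor.

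**Working it through.** The plan has no figure on this point to reproduce. Its sample size of 30 is borrowed from a previous study without an effect size or SD, and nothing below depends on that calculation. The documents give no SDs or correlations, so all distributional inputs are assumptions.

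**1. Shape of the NPRS baseline.** From the documents: scale 0-10, entry band 4-8. A whole-number score in that band takes five values. Its SD cannot exceed 2.0 (half at 4, half at 8) and is √2 = 1.41 if uniform. Truncating a normal variable (assumed mean 5-7, SD 1.5-2.5) to the band leaves SD 1.13-1.35, excess kurtosis -0.54 to -1.06, and skew up to 0.42 in size.

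**2. Type I error.** Simulation with 10,000 trials per setting, 15 per arm, four time points, baseline selected to 4-8, and scores rounded and clipped to 0-10. Assumed: underlying baseline mean 6, SD 2; follow-up SD 2-3; correlation 0.3-0.7; mean fall 2-4 points.
- Baseline SD is about 1.29, against 1.6-2.7 at follow-up.
- Between 2% and 30% of follow-up scores sit at 0.
- Sphericity epsilon is 0.94-1.00.
- Group-by-time F test at nominal 5%: 4.8-5.9% uncorrected, 4.1-4.9% with Greenhouse-Geisser.

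A second simulation (SD 2.2, 6,000 null trials) gave 5.3% and 5.6%.

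**3. Precision.** In an RM-ANOVA with baseline as a level, the treatment contrast of a follow-up visit against baseline is the difference in mean change. With baseline SD s0, follow-up SD s1 and observed correlation r, the per-patient variances are:
- change score: s0² + s1² − 2·r·s0·s1
- baseline as covariate: s1²·(1 − r²)
- difference between them: (s0 − r·s1)², which is never negative

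*Equal variances (s0 = s1).* The ratio is (1 − r²)/(2(1 − r)) = (1 + r)/2, so the cut is (1 − r)/2: 15% at r = 0.7, 25% at 0.5 and 35% at 0.3.

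*NPRS with the entry rule.* Assumed clinic mean 4-6, SD 2.2, same mean at follow-up, rounded scores, baseline kept if 4-8:

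| Clinic mean | Underlying correlation | s0 | s1 | Observed r | Change variance | Adjusted variance | Cut |
|---|---|---|---|---|---|---|---|
| 4 | 0.7 | 1.216 | 1.806 | 0.461 | 2.72 | 2.57 | 5% |
| 5 | 0.5 | 1.288 | 2.011 | 0.312 | 4.09 | 3.65 | 11% |
| 6 | 0.3 | 1.313 | 2.097 | 0.179 | 5.14 | 4.26 | 17% |

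For the last row: 1.313² + 2.097² − 2 × 0.179 × 1.313 × 2.097 = 5.14; 2.097² × (1 − 0.179²) = 4.26; 1 − 4.26/5.14 = 17%. For the mean of the three follow-up visits, the cut runs from 9% (mean 4, correlation 0.7) to 30% (mean 6, correlation 0.3). The NPRS gain per visit is smaller than under equal variances because a narrowed baseline adds less noise to a change score.

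**4. If the group main effect is tested instead.** Section 2.5 does not say which term carries the comparison. Averaging over four levels, one of them before treatment, dilutes a constant effect to about 3/4. In one simulated setting the estimate was -1.40 where the follow-up difference was -1.86 (1.40/1.86 = 0.75).

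**The case against.** **The p-values.** A reader might infer that a false assumption makes the tests invalid. The results above do not support that. RM-ANOVA needs normal residuals rather than normal raw scores, and although a truncated baseline gives non-normal residuals at that level, the error rate stays close to 5% across the assumed range.

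**Baseline as a time level.** A reader might infer that this is an error. In a randomized trial, testing group-by-time with baseline as a level is valid. Preferring baseline as a covariate is a matter of efficiency. It also does not follow from the normality sentence, so the two corrections stand separately.

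**Reach of the truncation.** NPRS is a secondary outcome. The entry rule does not directly truncate KOOS, the primary outcome, or PROMIS, and no floor or ceiling effect is shown for either. Even for NPRS the restriction may not be exact. Eligibility is screened at presentation on average pain over the past week, while baseline forms may follow up to 14 days later, so a recorded baseline could fall outside 4-8 if the two ratings differ. The NPRS form is not shown.

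**Size of the gain.** The 15-35% figure rests on equal variances and should not be carried over to NPRS. Estimating the slope also has a price: with 30 patients and a roughly normal baseline, it multiplies the expected variance by about 1 + 1/(30 − 4) = 1.038. At the weakest NPRS setting most of the gain goes (1 − 0.946 × 1.038 = 2%); at the strongest most of it remains (1 − 0.829 × 1.038 = 14%).

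**The hypotheses.** The aims and hypotheses also ask about improvement from baseline, and Hypothesis 1 at 3 months concerns only within-group change in both arms. A model of raw follow-up scores that simply drops baseline from the outcome would give no direct test of this. That objection stands, and the remedy has to meet it.

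None of this defends the sentence itself or supplies the missing check.

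**Conclusion.** The concern holds as a minor but worthwhile correction. The statement that standardized scales ensure normality is untrue for all three aims, and for NPRS it sits badly with the plan's own entry rule. Its effect on type I error is small (about 5-6% simulated). The practical cost is lost precision from a baseline score that is already collected for every outcome but not used as a covariate. Before the slope-estimation cost, the variance cut against change scores is about 5-17% per visit for NPRS and 9-30% for the three-visit mean. Under equal variances, which may suit KOOS and PROMIS, it is 15-35%.

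These sizes rest on assumed means, SDs and correlations and on complete data. The direction of the precision result (before that cost) does not depend on them, because the variance difference is a square.

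**What to change.** - Delete the normality sentence under Aims 1, 2a and 2b.
- For each outcome, model change from baseline at 3, 6 and 12 months with terms for group, visit, group-by-visit and the baseline score, using an unstructured covariance and Kenward-Roger degrees of freedom, given 15 patients per arm.
- Report the between-group contrast at each visit and the within-group mean change at each visit, so that the hypotheses about improvement from baseline are still tested.
- Pre-specify inspection of residuals, and give a permutation p-value for the treatment contrast as a sensitivity analysis.

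The cost is SAP wording, one model degree of freedom and a little analysis work. No extra data are needed and no study procedure changes.
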